 - ii. Questions on the mGCSI-DD are a 6-point Likert scale from 0 (none) to very severe (5) that address: nausea, retching, vomiting, stomach fullness, ability to finish a normal-sized meal, feeling excessively full after meals, loss of appetite, bloating, external assessment of stomach size, upper ab-dominal pain or discomfort.
- b. Secondary Endpoint
 - i. Breakthrough medication use: Defined as the change in the frequency of use of breakthrough medication, which is the medication that has been previously prescribed on an as-needed basis to manage symptoms.

Any change in frequency of use of breakthrough medications will be used as a secondary endpoint to assess for efficacy in the study.

 Bowel habits: Subjects will self report bowel habits during the baseline week and through the study period on the same questionnaire form. Since Senokot-S functions primarily as a mild bowel stimulant any significant change in bowel habits will help to assess for tolerability in this study.

IV. Study Design

The Phase II study design will be an open label, pre- and post-treatment assessment, prospective study. Sixty (60) study participants will be recruited over a 5-month period at a single site. Participants will be randomized into two treatment groups, a high- and low-dose, and will take medication dosed orally, twice daily or once daily at night.

V. Experimental Design, Methods, and Study Procedures

- **a.** Initial Identification of Potential Study Subjects Gastroenterologists who have agreed to refer their patient with diabetic gastroparesis for this study will make the initial contact with those patient (study inclusion/exclusion criteria will be provided to these physicians for ready reference). If the patient is interested in participating in the study the gastroenterologists will secure the patient's verbal permission to provide their name and contact information (phone or e-mail) to [name] or another member of the study team. The study team member will contact the patient and arrange a time to meet with them to explain the study and to answer any questions the potential subject may have.

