- b. Screening Visit The screening visit will include reviewing the participants' complete medical history after reviewing and obtaining informed consent. Data from the participant's medical history will be abstracted from the electronic medical record (EMR) and will be securely stored with other study-related data. Participants will be given the mGCSI-DD questionnaire and instructed on its use. At this visit participants will start recording their week of baseline scores by filling out a separate mGCSI-DD questionnaire and Breakthrough Medication Use and Bowel Habits documentation form daily.
- c. Visit 1 will occur 1 week after the screening visit. Participants will return with their mGCSI-DD baseline week of scores. They will be sequentially randomized (1:1) into either the high (8.6/50mg of senna/docusate taken by mouth twice daily) or low (8.6/50mg of senna/docusate taken by mouth once every night) dose study group. To reduce potential subject bias and placebo effect, participants will not be informed as to which dose of study medication they are randomized. They will be given their study medication and their 28-day mGCSI-DD questionnaire sheets, along with a pre-printed return envelope for use after completing their month of treatment in the study. They will be instructed to decrease use of any previously prescribed breakthrough medication as can safely be tolerated. Examples of these medication may include prokinetics such as Reglan (metoclopramide), erythromycin, or domperidone; anti-emtics such as Zofran (ondansetron), or Compazine (prochloperazine); or analgesics such as tramadol,

hydrocodone, or oxycodone. They will also be instructed to resume any breakthrough medication use as previously prescribed at the completion of the study and to continue routine follow ups with their care providers.

Subjects will be instructed to immediately contact the Principal Investigator if they experience episodes of significant diarrhea or rectal bleeding.

Participants may be notified by phone at the end of their study period to verify data or request missing data.

VI. Risks

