Senokot-S side effects. Known side effects of Senokot-S include diarrhea, nausea or vomiting, stomach pain, rectal bleeding, gas, abdominal bloating, and potential for allergic reaction such as skin rash. There have been safety concerns in the past about potential complications from long term use of stimulant laxatives like Senokot-S, such as cathartic colon, increased incidence of colorectal cancer, and liver disease. Several recent studies and reviews refute those previous conclusions and suggest long-term use of mild stimulant laxatives is likely safe when needed^{3,6,7}. Senokot-S is listed as pregnancy category C by the FDA. Women with child bearing potential will be required to use an effective form of birth control while participating in this study.

Ineffective treatment of diabetic gastroparesis. Since this medication has not yet been studied in the treatment of diabetic gastroparesis it is possible that symptoms of the disorder may worsen. The common symptoms of diabetic gastroparesis include nausea, vomiting, postprandial fullness, early satiety, and abdominal pain.

Loss of confidentiality. It is expected that this risk will be low because of numerous safeguards that will be in place, including standard data management procedures with Aurora Health Care.

VII. Benefits

A successful outcome in the proposed study will have immediate implications by reducing the symptoms of diabetic gastroparesis. Such a result will address the significant unmet need by providing a safe, inexpensive pharmacological therapy for a difficult to treat chronic disorder. These findings would allow patients to reduce or eliminate intake of the only FDA-approved therapeutic medication, Reglan[®], which has a black box warning and unfavorable side-effect profile. These known potential benefits are highly likely to outweigh the potential risks of the intervention in this study.

VIII. Study Population

Inclusion Criteria:

- Age 18-75 years, male and non-pregnant, non-lactating females
- Diagnosis of type 1 or type 2 diabetes mellitus
- Clinical diagnosis of diabetic gastroparesis

Exclusion Criteria:

- Diagnosed idiopathic gastroparesis
- A history or inflammatory bowel disease, such as Crohn's disease or ulcerative colitis
- A history of bowel obstruction, current unexplained abdominal pain, or undiagnosed rectal bleeding
- Gastrointestinal cancer
- Any active cancer
- Prior gastric surgery
- End-stage heart disease, liver disease, lung disease

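### Cheap improvement: add allergic reaction and severe vomiting to the immediate-contact instruction in V.c, and record why participants stop study drug

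*Combined protocol and SAP*

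**What the plan says.** Section V.c (Visit 1) contains the only immediate-contact instruction in the protocol body: "Subjects will be instructed to immediately contact the Principal Investigator if they experience episodes of significant diarrhea or rectal bleeding".

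Section VI lists wider risks. Known side effects "include diarrhea, nausea or vomiting, stomach pain, rectal bleeding, gas, abdominal bloating, and potential for allergic reaction such as skin rash". Under ineffective treatment, it adds that "it is possible that symptoms of the disorder may worsen", and it counts vomiting among the common symptoms of the disorder.

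V.c also says of rescue drugs: "They will be instructed to decrease use of any previously prescribed breakthrough medication as can safely be tolerated". Its examples include prokinetics, anti-emetics and analgesics.

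On the flow of information:

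- The diary has items "that address: nausea, retching, vomiting, stomach fullness" and others, including bloating and upper abdominal pain (Study End Points). Participants receive a "pre-printed return envelope for use after completing their month of treatment in the study" (V.c).
- After Visit 1 the only study contact described is optional: "Participants may be notified by phone at the end of their study period to verify data or request missing data" (V.c).
- Participants are told "to continue routine follow ups with their care providers" (V.c). They may stop whenever they wish and go back to earlier treatment (Section XIII).
- Section XI lists medical history, mGCSI-DD forms, and medication and bowel-habit forms. Its REDCap paragraph adds demographics and the use of study and breakthrough medication.
- Section XIII gives safety monitoring to the research office and investigator, and makes a negative trend in post-treatment diary scores a stopping point. Section XIV refers to the IRB's reporting SOPs.

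**The concern.** A participant who follows V.c as written is told to call for two bowel events. A rash, or vomiting that becomes severe while anti-emetics are being reduced, is a risk that the protocol foresees but does not ask to hear about promptly. The phrase about what can safely be tolerated leaves that judgement with the participant and attaches no request to call if it goes badly.

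There are two consequences. First, those responsible for safety monitoring under Section XIII have no instructed route, within the protocol body, to timely news of these events. Second, the dose comparison loses information. Section II randomizes to two doses partly to judge tolerability and aims to choose between them. A participant who stops because of a rash and one who stops for lack of benefit would look alike in the listed data, yet they mean different things for dose selection.

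**Working it through.** There is no stated figure to reproduce and no event rate to compute with. The check sets the risks named in Section VI against three things: the V.c contact instruction, the listed data, and the time at which those data reach the team.

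| Risk or event | Immediate contact under V.c? | Described as recorded? | When the team would learn of it |
|---|---|---|---|
| Marked diarrhea | Yes | Bowel habits form (items not shown) | At once, if the instruction is followed |
| Rectal bleeding | Yes | Not stated (bowel form items not shown) | At once, if the instruction is followed |
| Nausea, vomiting, bloating, stomach pain | No | mGCSI-DD, daily (pain as the upper abdominal item) | When the diary is returned after the month |
| Worsening gastroparesis | No | mGCSI-DD, daily | When the diary is returned after the month |
| Gas | No | Not stated (bowel form items not shown) | Not stated; no prompt call needed |
| Allergic reaction | No | No listed form or dataset | Only if volunteered, or raised at the optional call |
| Stopping study drug | No | Study-medication use may show it | Not stated |
| Reason for stopping | No | No listed form or dataset | Only if volunteered, or raised at the optional call |

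Reading down the table:

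1. **Prompt notice.** For vomiting and worsening symptoms the data are captured; what is missing is a timely alert. Scheduled contacts during the 28 days of treatment: 0.
2. **The Section XIII stopping point.** It looks at a trend in post-treatment scores, and those scores come from diaries returned after treatment. It could protect later enrollees. It cannot flag a participant who is worsening now.
3. **Capture.** Two things appear nowhere in the listed forms or datasets: allergic reaction and the reason for stopping. The mGCSI-DD items are all gastroparesis symptoms, and a bowel-habits form would not be expected to ask about rash (an assumption, since the form is not reproduced).
4. **Which omissions matter.** Gas, mild bloating and usual disease symptoms do not warrant an immediate call. That leaves allergic reaction and severe vomiting as the triggers worth adding, and one data item for reasons.

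**The case against.** The strongest reply is that participant instructions may sit in the consent form, which is absent from our copy, and in IRB procedures that we cannot see. V.c's two triggers are also a defensible choice: they are bowel events that the symptom diary does not ask about, while vomiting, pain and bloating are scored every day. Section XI's list may not be exhaustive. This stands as a limit: the point concerns the protocol body only. It does not remove the gap, because V.c states a positive rule with two named triggers, and a daily diary that is mailed back afterwards gives no prompt alert.

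Four stronger readings are tempting, and the documents do not support them.

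- *The instruction covers only 2 of 8 named side effects, so three quarters are neglected.* The fraction is a poor measure. Four of the six others are daily diary items, and several of the six should not prompt a call at all.
- *Stops would go unnoticed when the doses are compared.* The stored study-medication data may show them by arm. Only the reason is not described as recorded.
- *Participants are left without recourse.* They may stop, resume earlier treatment, see their own providers or call unprompted.
- *Worsening is unmonitored.* The primary instrument and the Section XIII stopping point both address it, though not promptly for an individual.

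A looser trigger, such as symptoms clearly worse than in the baseline week, would also be hard to apply. Participants hand in their baseline diaries at Visit 1, and they are reducing rescue medication.

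**Conclusion.** The point holds as a modest improvement. As written, the protocol body asks for no prompt report of an allergic reaction or severe vomiting, and no listed form or dataset is described as recording an allergic reaction or why a participant stopped. Both matter to a study that states tolerability by dose as an aim.

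Its size is two missing contact triggers and one missing data item, in a 28-day treatment period with no scheduled contact. No frequency, probability or harm is estimated, because the documents give no event rates.

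The conclusion assumes that the forms contain what their titles and the mGCSI-DD item list suggest, and that neither the consent form nor the IRB procedures already carry the wider instruction. If the consent form does, what remains is to bring V.c into line with it and to record the reasons.

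**What to change.** Check the consent form first. If it is already broader, align V.c with it. Otherwise:

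1. Extend the V.c contact sentence to add signs of allergic reaction (such as rash), and severe or persistent vomiting or inability to keep food or fluids down. Leave out gas, mild bloating and usual disease symptoms.
2. Add a sentence asking participants who stop study drug to tell the team why.
3. Add one item to Section XI: date, event or reason, and arm. Complete it whenever such a contact or stop occurs, ask about it at the end-of-study call that V.c already allows, and summarise it by arm as tolerability data. Because that call is optional, the arm summary will be like for like only if all participants are asked (at most 60 short calls).

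The cost is a few lines of protocol text, matching consent wording, one data field and some extra calls, whose number cannot be estimated from the documents. No visit is added, and the primary mGCSI-DD endpoint is unchanged.

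### Current diarrhea is not an exclusion and no one is told to look at the baseline bowel record before dispensing, so a participant with active diarrhea is eligible for a planned 28 days of senna/docusate

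*Combined protocol and SAP*

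**What the plan says.** All references are to the combined protocol and SAP.

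- **Eligibility (VIII).** There are 3 inclusion and 11 exclusion bullets. The one closest to this point is "A history of bowel obstruction, current unexplained abdominal pain, or undiagnosed rectal bleeding". Other bowel-related exclusions are inflammatory bowel disease, gastrointestinal cancer, and use of senna or docusate now or in the preceding 3 months.
- **Drug effect ((c) Study End Points; VI).** The bowel-habits endpoint is justified thus: "Since Senokot-S functions primarily as a mild bowel stimulant any significant change in bowel habits will help to assess for tolerability". Section VI puts diarrhea first in its list of known side effects.
- **Baseline record ((c) Study End Points; V.b).** "Subjects will self report bowel habits during the baseline week and through the study period on the same questionnaire form". From the screening visit onward, participants begin "filling out a separate mGCSI-DD questionnaire and Breakthrough Medication Use and Bowel Habits documentation form daily".
- **Screening (IX).** Final screening is finished at the in-person screening visit, together with consent.
- **Visit 1 (V.c).** One week later, "Participants will return with their mGCSI-DD baseline week of scores". Randomisation, dispensing and instructions follow.
- **After Visit 1 (V.c; XIII).** Participants are told to "immediately contact the Principal Investigator if they experience episodes of significant diarrhea or rectal bleeding". They receive their diary sheets "along with a pre-printed return envelope for use after completing their month of treatment in the study". Then: "Participants may be notified by phone at the end of their study period to verify data or request missing data". Section XIII assigns safety monitoring to the research office and the principal investigator, and lets participants withdraw freely.

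**The concern.** A laxative whose leading listed side effect is diarrhea is to be given to people who have not been checked, under any written rule, for diarrhea they already have. The study collects the relevant information in the week before treatment, but no step connects it to the decision to treat.

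What is at stake is participant safety: a planned 28 days of a bowel stimulant in someone with active diarrhea. No sample size, error rate or other stated figure is affected.

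**Working it through.** The plan states no figure on this point, so the check is a reading of the criteria followed by the order of events.

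**1. Do the criteria cover it?** Inclusion: 3 bullets (age and sex; diabetes; clinical gastroparesis), 0 of which mention diarrhea, stool frequency or stool consistency. Exclusion: 11 bullets, again 0. The inflammatory bowel disease bullet removes one possible cause of diarrhea, and the senna/docusate bullet removes people recently exposed to the study drug's ingredients. Neither removes diarrhea as such.

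**2. Does the sequence of visits cover it?**

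| Step | Section | What is known about bowel habits | Stated eligibility action |
|---|---|---|---|
| Referral and remote screening | V.a, IX | Whatever the clinician or the record shows | Criteria applied; none concerns diarrhea |
| Screening visit | V.b, IX | Medical history; baseline record only now starting | Final screening completed here |
| Baseline week | V.b | About 7 daily bowel records | None |
| Visit 1 | V.c | Baseline week complete | None; randomised and drug dispensed |
| 28 treatment days | V.c | Daily self-report | No visit described |
| After treatment | V.c | Forms posted back; possible call about data | Too late |

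Eligibility is settled before the baseline bowel record exists and is not reopened once it does. Section V.c names only the mGCSI-DD scores as returned at Visit 1. Because the endpoint section speaks of the same questionnaire form, the bowel data may well come back at the same time, but no one is told to read them. Their stated use is to assess tolerability.

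**3. Does a later rule catch it?** The stopping points in XIII are the end of the 5-month period and an adverse trend in mGCSI-DD scores. The mGCSI-DD items listed in the endpoint section do not include diarrhea. The call instruction in V.c depends on the participant and has no hold or withdrawal action attached.

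**4. Planned exposure.** Low dose: 28 days × 1 = 28 doses of 8.6/50 mg. High dose: 28 days × 2 = 56 doses.

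**5. Would an exclusion remove the target population?** Section VI lists the common symptoms of diabetic gastroparesis, and diarrhea is not among them. The exclusion would therefore not remove people for the listed symptoms under treatment. That list covers common symptoms only, so some narrowing remains possible.

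**6. Number affected.** No rate of baseline diarrhea is given, so no share of the 60 participants can be calculated.

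**The case against.** The strongest reply is that being eligible is not the same as being enrolled, and that planned exposure is not actual exposure. Each participant comes through a gastroenterologist, a record review and an in-person history, and nothing obliges these clinicians to enrol everyone who meets no exclusion. The dose is low. The call instruction is not limited to new diarrhea, so it also reaches someone who had significant diarrhea at the start. Participants can stop when they wish.

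All of this stands as a limit on the size of the problem. It does not close the gap. The referring physicians work from a criteria list that omits diarrhea, so holding a patient back rests on unwritten judgment, and the remaining protections operate only after the drug has been handed over.

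A further fair point is that an exclusion narrows the population in which tolerability is learned, in a study that aims to span mild to severe disease. That is a real cost, though a small one.

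Two stronger readings should be resisted:

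- A reader might infer that participants with diarrhea will be enrolled and left on drug for 28 days without protection. The documents do not support this: safeguards exist, and 28 days is the planned duration, not a compelled one.
- A reader might infer, because undiagnosed rectal bleeding is both an exclusion and a reason to call, that diarrhea was meant to be treated alike. That bullet sits with unexplained abdominal pain and is better read as screening for undiagnosed pathology. It shows no policy of matching each call event with an exclusion.

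**Conclusion.** The gap is real and should be closed, as a modest safety correction. None of the 14 eligibility bullets (3 + 11) addresses current diarrhea, and no stated step between the baseline bowel record and dispensing requires staff to look at it. Following the plan as written, a participant with active diarrhea may be given 28 or 56 planned doses of senna/docusate. Visit 1 is the last scheduled visit described, and so the last scheduled visit at which staff could withhold the drug using data already being collected.

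The harm is unquantified: the number affected is unknown, the dose is low and partial safeguards exist. The conclusion rests on the written criteria and procedures. It assumes no unwritten site practice, and it makes no claim about how often such a participant would be referred.

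**What to change.** 1. **VIII:** add an exclusion such as *Current diarrhea, by history at screening or on the baseline bowel-habits record*, with a numerical threshold fixed before enrolment. As an assumption for the investigator to confirm, this could be at least 3 loose stools per day on at least 3 of the 7 baseline days.
2. **V.c:** have participants bring the baseline bowel-habits form to Visit 1 and have staff check it against the exclusion before randomisation. If the exclusion is met, the participant is not randomised and no drug is dispensed.
3. **IX:** make eligibility provisional at the screening visit and confirmed at Visit 1 after that check.

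**Cost.** One exclusion line, a short addition to V.c and one amended sentence in IX, with no new visit or test. The form must record loose stools; its content is not in the documents, so it may need an extra item. Some participants, in a number that cannot be estimated, may be excluded after completing the baseline week, and tolerability will be studied in a slightly narrower population.

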AURORA HEALTH CARE, INC.

PROTOCOL TITLE: Pilot study for the efficacy and tolerability of Senokot-S[®] in the treatment of diabetic gastroparesis

PRINCIPAL INVESTIGATOR:

[name] Hospitalist [name] [contact] [contact] Email: [contact]

INVESTIGATORS AND KEY PERSONNEL:[name], [name], [name]

This protocol was designed and developed by Aurora Healthcare, Inc. It is intended to be used only in conjunction with institution-specific IRB approval for study entry.

I. Background and Significance

Diabetic gastroparesis can be a difficult-to-treat complication of longstanding diabetes that can significantly compromise quality of life in those affected. Today there is only one medication approved by the FDA for the indication of diabetic gastroparesis and it has received a black box warning due to potential for severe neurological side effects. There are other medications that have found some success in the treatment of diabetic gastroparesis, but they also have the potential for serious side effects, and some are only available through a special use program.¹

II. Specific Aim

The aim of the study is to evaluate the efficacy of the stimulant laxative Senokot-S[®] for the treatment of diabetic gastroparesis. Senokot-S, and its metabolites, are thought to produce peristalsis, drive intra-luminal fluid and electrolyte shifts, and have an irritant effect on the gut mucosa^{2,3}. These complex physiologic mechanisms appear may sufficiently promote stomach emptying, and thereby reduce or eliminate the severity of gastroparesis symptoms. In this open label study, participants will be randomized into high and low dose groups to assess for ideal dosing and tolerability. It is the overall goal of this study to select the most promising dose-strength for the treatment of mild through severe gastroparesis.

(c) Study End Points

- a. Primary Endpoint
 - i. Modified GCSI-DD: Subjects will complete the modified Gastroparesis Cardinal Symptom Index-Daily Diary (mGCSI-DD)^{4,5}. The mGCSI-DD is a validated patient reported outcome (PRO) instrument with excellent testretest reliability, and will be used as the primary instrument to assess for efficacy in this study.

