Access to data housed in REDCap Cloud and associated with this research study will be limited to those individuals listed on the IRB approved research study, as well as caregivers from Research Analytics for administrative reasons. Study team members access to the system and the data itself will be limited in accordance with need (i.e., biostatisticians may be limited to simply export the dataset to statistical tools, research coordinators may be limited to entering data, etc.). Overall, limiting access to study team members by need should reduce the risk of accidental disclosure and breach of confidentiality. However, using a cloud-based application may incidentally raise the risk of a breach in confidentiality, and, therefore, Aurora Health Care, Inc. has negotiated strong protections with the vendor in the event of a breach of confidentiality.

XII. Statistical Plan

All category and continuous variables will be described using appropriate descriptive statistics such as frequency, percentage for category variables and mean, standard deviation, median, and range for continuous variables. Pre and post outcomes variables for two groups of patients in the experimental groups will be compared using appropriate parametric and/or non parametric statistical tests. For all statistical tests an alpha level of 0.05 will be used and all statistical analysis will be carried out using SAS version 9.4, SAS Institute, Cary, NC.

XIII. Monitoring Plan

Data monitoring, safety monitoring, and statistical analysis will be done through the research office and principal investigator.

Participants can stop the study at any time for any reason and can resume previous treatments whenever needed. Stopping points will be at the end of the 5 month study period or if a negative trend in mGCSI-DD post-treatment scores is observed.

XIV. Regulatory Requirements

The investigators and all key personnel agree to abide by the determinations of the Aurora IRB, including obtaining documented informed consent prior to inclusion of any individual in this research study. The investigators and all key personnel will comply with reporting requirements as outlined in the Aurora IRB Standard Operating Procedures (SOPs). In addition, investigators will permit access for on-site monitoring by representatives of the Aurora IRB, the Aurora Research Institute Investigator-Initiated Research unit, and the Aurora Research Institute Quality Improvement Program.

XV. References

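### Section XII does not commit to using the baseline diary week as a covariate, so the high-versus-low dose difference may be estimated less precisely than the data allow

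*Combined protocol and SAP*

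**What the plan says.** Section II sets dose selection as the overall goal, so the contrast that matters most is high against low dose. Section IV fixes the size: "Sixty (60) study participants will be recruited over a 5-month period at a single site". Section V.c gives the allocation: "They will be sequentially randomized (1:1) into either the high" or the low dose group.

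The baseline is collected before allocation. In V.b, "At this visit participants will start recording their week of baseline scores by filling out a separate mGCSI-DD questionnaire", together with a daily breakthrough-medication and bowel form. In V.c, "Participants will return with their mGCSI-DD baseline week of scores", and randomisation follows at that visit. Participants then receive 28 days of diary sheets.

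The only sentence in Section XII on comparison says that pre and post outcomes for the two groups "will be compared using appropriate parametric and/or non parametric statistical tests". On error rate it adds: "For all statistical tests an alpha level of 0.05 will be used". No covariate, regression, ANCOVA or mixed model appears anywhere in the document. No change-score, paired or post-only test is named either.

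**The concern.** The baseline week has already been paid for in participant effort, and its only visible analysis role is as the pre value. In a design labelled pre- and post-treatment assessment, the natural reading of XII is that each participant's change is computed and the changes are compared between arms. That forces the baseline slope to equal 1. When the true slope is lower, the change score carries extra baseline noise into the dose difference. A comparison of post values alone forces the slope to 0 and ignores the baseline. ANCOVA estimates the slope.

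With about 30 per arm, precision is scarce, and the width of the interval for the dose difference limits how well this trial can choose a dose. There is a second cost. If the outcome form (post or change) and the test (t or rank) are both left open, several p-values are available for one question.

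**Working it through.** **Inputs from the document.** N = 60 (IV) and 1:1 allocation (V.c), so n = 30 per arm if all 60 are randomised. Alpha is 0.05 (XII). The document gives no effect size, SD, power or dropout rate behind the 60, so there is no planned figure to reproduce.

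**Assumptions.** Two-sided alpha, no dropout, equal SD of the baseline and on-treatment means, and a correlation r between them. The document does not give r, so a range is shown. The illustrative true dose difference is 0.5 SD.

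**Variance of the dose difference, relative to a post-only test (= 1).**
- Change score: 2(1−r)
- ANCOVA: 1−r²
- ANCOVA against change score: (1−r²)/[2(1−r)] = (1+r)/2

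Example at r=0.5: the change factor is 2×0.5 = 1.00 and the ANCOVA factor is 1−0.25 = 0.75. The SE ratio is √0.75 = 0.866, a 13% cut, and 60/0.75 = 80 participants' worth of information.

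| | r=0.3 | r=0.5 | r=0.7 | r=0.8 |
|---|---|---|---|---|
| Change-score variance factor | 1.40 | 1.00 | 0.60 | 0.40 |
| ANCOVA variance factor | 0.91 | 0.75 | 0.51 | 0.36 |
| SE cut against change score | 19% | 13% | 8% | 5% |
| SE cut against post-only | 5% | 13% | 29% | 40% |
| 60 under ANCOVA equals, under change score | 92 | 80 | 71 | 67 |
| Detectable difference at 80% power, change score (SD) | 0.86 | 0.72 | 0.56 | 0.46 |
| Detectable difference at 80% power, ANCOVA (SD) | 0.69 | 0.63 | 0.52 | 0.43 |

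The detectable difference is (1.960+0.842)×√(2/30) = 0.723 SD for a post-only test, multiplied by the square root of the variance factor for the others.

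**Power at 0.5 SD, 30 per arm.** The normal approximation gives, for change score then ANCOVA, 49% and 61% at r=0.5, and 71% and 77% at r=0.7. Simulation with bivariate normal data (6,000 runs per setting) gives slightly lower values: 36% and 50% at r=0.3, 48% and 59% at r=0.5, 70% and 76% at r=0.7, 85% and 88% at r=0.8. Post-only power is 47–48% throughout.

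**Cost of estimating the slope.** About 1/(2n−4) = 1/56, or 2% in variance. At r=0.5 the factor 0.75 becomes 0.763.

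**If the SDs differ.** Let k be the baseline SD divided by the on-treatment SD. The change-score factor is 1+k²−2rk = (1−r²)+(k−r)². The excess over ANCOVA is (k−r)², which is never negative, so ANCOVA is at worst equal apart from the slope cost. The size does move. Taking k = 0.9 and 1.1 as illustrations at r=0.5, the factors are 0.75+0.16 = 0.91 and 0.75+0.36 = 1.11, and the SE cuts are 1−√(0.75/0.91) = 9% and 1−√(0.75/1.11) = 18%.

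**Open choice of analysis.** Under no dose effect, reporting the smallest p of four tests (t and rank, on post and on change) gives 10–11% false positives in simulation. Choosing only between t and rank on a single outcome gives about 5–6%. Most of the inflation therefore comes from the post/change choice.

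**The case against.** The strongest reply is that XII excludes nothing. ANCOVA is a parametric method, it fits the sentence, and SAS 9.4 runs it. A reader might infer that the plan has decided against baseline adjustment, or that precision is certain to be lost. The text supports neither: XII is silent, so the loss is a risk whose size depends on an unnamed test and an unknown r. This part of the reply stands.

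Three other strong readings also go too far.

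- **The post-only gain as the headline.** At r=0.7, 60/0.51 is about 118 participants' worth. That assumes the baseline is discarded, which sits badly with a pre/post design and with a breakthrough-use endpoint defined as a change.
- **Doubling of false positives through the phrase allowing either test family.** That choice alone adds about one percentage point at most.
- **Analysis by the principal investigator alone.** XIII says "Data monitoring, safety monitoring, and statistical analysis will be done through the research office and principal investigator", and XI foresees biostatisticians with restricted export access.

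Two further points are fair. Change-score and post-only differences are both unbiased under randomisation, so the issue is precision, plus chance imbalance in the particular sample. And this is a pilot in which the contrast, the summary score and the analysis window are also undefined, so covariate adjustment refines a primary analysis that still has to be stated.

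The reply does not remove the point. Because r is unknown, neither simpler test can be chosen safely in advance: change scores do badly at low r and post-only does badly at high r. A plan that merely permits the efficient analysis does not secure it.

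**Conclusion.** The point holds as a gap in commitment, not as an error in a named method. If XII is carried out as a change-score comparison, the SE of the dose difference is larger than necessary, and ANCOVA would cut it by about 19% at r=0.3, falling to 5% at r=0.8. Against a post-only test the gain is larger than this once r exceeds 0.5. If the eventual test is a change score and r is 0.8 or more, the gain is small.

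These sizes rest on equal pre and post SDs, 30 evaluable per arm, two-sided testing and an assumed r. They concern the between-dose contrast only, not within-arm pre/post tests. The 10% false-positive figure applies only if the most favourable of the four analyses were reported. The trial can run without the change, but the change should be made because it uses data already being collected.

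**What to change.** In Section XII, before any outcome data are seen, replace the general sentence with one primary between-dose model: linear regression of each participant's mean on-treatment mGCSI-DD over the 28 diary days on randomised arm and that participant's own baseline-week mean. Report the high-minus-low difference with its 95% CI. State how the daily items are combined into a score, and use the same rule for both periods. Name one rank-based test as a sensitivity analysis only.

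For breakthrough-medication frequency and bowel counts, also adjust for the baseline value, but with a model suited to counts; the linear model does not carry over automatically.

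The cost is one degree of freedom (about 2% in variance) and a few lines of text. No participants, visits or forms are added.
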